15.0 Potential Benefits to Subjects

15.1 Describe the potential benefits that individual subjects may experience from taking part in the research. Include as may be useful for the IRB's consideration, the probability, magnitude, and duration of the potential benefits.

Participants receiving the study drug may see improvement in their MD symptoms and quality of life. It is possible, however, that participants will receive no direct health benefit from being in this study. Others may benefit from the information learned. The results of this study could support a minimally invasive, tolerable and efficacious treatment for those who suffer from Ménière's disease. Risks to the current study's participants are reasonable in relation to the importance of the knowledge gained. Many of the current alternative treatments for Ménière's disease are much higher in risk than the treatment proposed by this study. The improvement of symptoms and quality of life could also be greater than available treatments. Although this is just a pilot-of-proof study, the evidence could argue for larger clinical studies in the future that then support FDA review of the new indication and, eventually, approval of the new indication. Subsequently, the efficient and low-risk medication would be made available to MD patients at affordable costs shared with insurance companies. Additionally, the results of the study would support research into a new etiology theory of Ménière's disease.

15.2 Indicate if there is no direct benefit. Do not include benefits to society or others.

Response: N/A

16.0 Vulnerable Populations

16.1 If the research involves individuals who are vulnerable to coercion or undue influence, describe additional safeguards included to protect their rights and welfare.

- If the research involves pregnant women, review "CHECKLIST: Pregnant Women (HRP-412)" to ensure that you have provided sufficient information.
- If the research involves neonates of uncertain viability or nonviable neonates, review "CHECKLIST: Neonates (HRP-413)" or "HRP-414 – CHECKLIST: Neonates of Uncertain Viability (HRP-414)" to ensure that you have provided sufficient information.
- If the research involves prisoners, review "CHECKLIST: Prisoners (HRP-415)" to ensure that you have provided sufficient information.
- If the research involves persons who have not attained the legal age for consent to treatments or procedures involved in the research ("children"), review the "CHECKLIST: Children (HRP-416)" to ensure that you have provided sufficient information.
- If the research involves cognitively impaired adults, review "CHECKLIST: Cognitively Impaired Adults (HRP-417)" to ensure that you have provided sufficient information.
- Consider if other specifically targeted populations such as students, employees of a specific firm or educationally/economically disadvantaged persons are vulnerable to coercion or undue influence. The checklists listed above for other populations should be used as a guide to ensure that you have provided sufficient information.

Response: N/A

17.0 Community-Based Participatory Research

17.1 Describe involvement of the community in the design and conduct of the research.

Response: N/A

Note: "Community-based Participatory Research" is a collaborative approach to research that equitably involves all partners in the research process and recognizes the unique strengths that each brings. Community-based Participatory Research begins with a research topic of importance to the community, has the aim of combining knowledge with action and achieving social change to improve health outcomes and eliminate health disparities.

18.0 Sharing of Results with Subjects

18.1 Describe whether or not results (study results or individual subject results, such as results of investigational diagnostic tests, genetic

tests, or incidental findings) will be shared with subjects or others (e.g., the subject's primary care physicians) and if so, describe how it will be shared.

Response:

Results of screening tests that are relevant to the patient's routine medical care will be shared with the patient as they are conducted. All testing that is part of routine medical care (prior to randomization), and not specific to study-related testing, is automatically copied to the patient's primary doctor, unless the patient requests additional or alternative CCs. No study-specific testing or outcomes are communicated to the patient, their primary doctor, or anybody who is not on the protocol. The only exception to this is in the extremely unlikely event that study-specific tests reveal a risk to the participants' health, such as abnormal blood or urine test results, in which case the participant will be informed immediately.

The participant will be informed in a timely manner by the investigator or research personnel when new information becomes available that may be relevant to the participant's willingness to continue participation in the trial. This may be done in writing by letter, revised ICF or in any manner approved by the reviewing IRB. The communication of this information should be documented in the medical record along with a copy of the information provided.

19.0 Setting

19.1 Describe the sites or locations where your research team will conduct the research.

All site visits will be conducted at the Dent Neurologic Institute. The Dizziness and Balance Center (DBC) is well outfitted with the necessary audio testing equipment. This equipment is regularly maintained for clinical use. The space within the DBC will provide private exam rooms and check out areas for informed consent, questionnaires and other study procedures. The Dizziness and Balance Center will also provide access to a patient population for recruitment purposes. Blood samples will be collected, centrifuged and packed before being shipped for analysis in the Dent Neurologic Institute Infusion Clinic located within the Dent Neurologic Institute. In addition to the study space and equipment available at Dent, the organization serves as a resource for research design and implementation. Research staff has insured that all study personnel have undergone the appropriate training for human subjects research. The Dent Neuroscience Research Center, also located within the same building, is composed of experts with years of research experience that can guide and assist the study team. Other personnel at Dent include experienced pharmacists, audiologists and psychiatrists, all of whom the PI has built consultation relationships with over several years. Lastly, the Dent is funding one of the staff members to work on the execution of the study full-time.

Kaleida Health Laboratory is located only a four-minute drive away from Dent Neurologic, making the shipping and processing of blood samples simple and easy. The clinical laboratory leads Western New York in quick and accurate testing, performing more than 4 million tests each year. Kaleida Health's experienced laboratory scientists, couriers and computer system will ensure that the blood analysis for the study is done in an exceptional manner. Although a contract will only be created once the study receives IRB and funding approval, the Dent Neurologic Institute has successfully worked with Kaleida Health in the past.

UBSoPPS Research Pharmacy is a licensed pharmacy that provides the expertise of a licensed pharmacist to assist clinicians in conducting clinical studies. The Pharmacy allows the investigating clinician to conduct blinded studies involving placebos and encapsulates drug preparations in various design patterns. The facility can compound specific drug strengths that may not be available commercially, thereby giving the clinician more control over the strengths of the drug they wish to investigate. All research is conducted in an ethical manner with its focus on protecting the human subjects and complying with all HIPAA regulations. Budget planning is provided and assistance in statistical design is available.

The UB Statistical Consulting Laboratory provides doctorate level expertise in biostatistics and clinical research. This collaboration will strengthen the design of the study and the subsequent conclusions made from the study's results.

19.2 Identify where your research team will identify and recruit potential subjects.

Response: The study hopes to recruit from the patient population at the Dent Dizziness and Balance Center and [name] patients at Buffalo ENT Specialists. In doing so, the PI and staff will have to access medical charts/records to verify eligibility and diagnosis of Meniere's disease prior to obtaining consent of potential participants. The study needs information from preexisting medical records to identify a candidate pool based on specific criteria applied to those records. Obtaining a signed authorization prior to recruitment is not practicable. If an authorization form was given to every patient seen in the Dizziness and Balance Center and every one of [name] patients, the time needed for recruitment would be dramatically increased and potential eligible participants could be overlooked due to their next appointment being scheduled for months later. Additionally, the information we are looking to capture was not collected for research purposes. This information already exists within patients' charts and patients have already consented to [name] and the staff of the Dizziness and Balance Center or [name] to have access to this information as part of their standard care. Once eligible potential participants are identified they will be sent a letter, which gives an overview of the study and contact information if they are interested in enrolling.

A referral letter will also be sent to area physicians and ENT specialists informing them of the study design and inclusion/exclusion criteria. Those receiving the letter are encouraged to notify eligible patients of the opportunity to participate and how to contact the study staff if they are interested.

If enrollment numbers are not met through this method, recruitment strategies will include an advertisement in the once monthly issue of an After 50 free newspaper, 32 sixty-second radio advertisements and 50 sixty-second streaming commercials for two weeks. The study has requested funds for this purpose, but is hoping to exhaust all other potential participants within the Dizziness and Balance Center and [name] patients first. Therefore, the additional newspaper and radio advertisement recruitment materials will be submitted as an amendment at a later date.

19.3 Identify where research procedures will be performed.

Response: Research Procedures with participants will be performed at Dent Neurologic Institute, within the Dizziness and Balance Center (DBC).

19.4 Describe the composition and involvement of any community advisory board.

Response: N/A

- 19.5 For research conducted outside of the organization and its affiliates describe:
 - Site-specific regulations or customs affecting the research for research outside the organization.
 - Local scientific and ethical review structure outside the organization.

Response: Please see section 19.0 for site specific procedures/policies/regulations for the pharmacy, laboratory, and statistical computing sites.

20.0 Resources Available

20.1 Describe the qualifications (e.g., training, experience, oversight) of you and your staff as required to perform their role. When applicable describe their knowledge of the local study sites, culture, and society. Provide enough information to convince the IRB that you have qualified staff for the proposed research. Note- If you specify a person by name, a change to that person will require prior approval by the IRB. If you specify people by role (e.g., coordinator, research assistant, co-investigator, or pharmacist), a change to that person will not usually require prior approval by the IRB, provided that person meets the qualifications described to fulfill their roles.

Response:

Study coordinator: College degree or applicable technical training, Mathematics/statistics skills, prior research experience, proficiency in Microsoft Office, CITI and HIPAA training, strong interpersonal and communication skills, excellent organizational skills, problem-solving skills, high level of communication through written form.

Co-PIs: College degree or applicable technical training, proficiency in Microsoft Office, CITI and HIPAA training, strong interpersonal and communication skills, excellent organizational skills.

Other research staff: Excellent oral and written communication skills, including listening skills for participant concerns and communications, some basic knowledge of the research protocol and related literature, CITI and HIPAA training

Describe other resources available to conduct the research: For example, as appropriate:

20.2 Justify the feasibility of recruiting the required number of suitable subjects within the agreed recruitment period. For example, how many potential subjects do you have access to? What percentage of those potential subjects do you need to recruit?

Response: While Meniere's Disease affects approximately 20-200 out of every 100,000 people, at this specialized institute, [name] sees approximately 70-100 Meniere's Disease patients per year. Therefore, we believe it is reasonable to obtain the 12 participants (or approximately 5-10% of these patients) who meet eligibility criteria over the next 1-2 years.

20.3 Describe the time that you will devote to conducting and completing the research.

Response: The study coordinator will work on the study full time at 40 hours per week. The remaining research staff will spend, on average, approximately 3-5 hours per week each on the research study. The pharmacy has allocated 21 pharmacist hours, and the statistician has allocated 20 towards this pilot study.

20.4 Describe your facilities.

Response: The Dizziness and Balance Center (DBC) is well outfitted with the necessary audio testing equipment. This equipment is regularly maintained for clinical use. The space within the DBC will provide private exam rooms and check out areas for informed consent, questionnaires and other study procedures. The Dizziness and Balance Center will also provide access to a patient population for recruitment purposes. Blood samples will be collected, centrifuged and packed before being shipped for analysis in the Dent Neurologic Institute Infusion Clinic located within the Dent Neurologic Institute. In addition to the study space and equipment available at Dent, the organization serves as a resource for research design and implementation. Research staff has insured that all study personnel have undergone the appropriate training for human subjects research. The Dent Neuroscience Research Center, also located within the same building, is composed of experts with years of research experience that can guide and assist the study team. Other personnel at Dent include experienced pharmacists, audiologists and psychiatrists, all of whom the PI has built consultation relationships with over several years.

20.5 Describe the availability of medical or psychological resources that subjects might need as a result of an anticipated consequences of the human research.

Response: Routinely, the Buffalo General Hospital, Erie County Medical Center, Millard Fillmore Hospital and/or the University at Buffalo, State University of New York, Dent Neurologic Institute, their agents employees do not compensate for or provide free medical care for human subjects/participants in the event that any injury results from participation in a human research project. In the unlikely event that a participant become ill, injured, or requires psychological services as a direct result of participating in this study, they may receive the appropriate medical care at the location of their choosing.

20.6 Describe your process to ensure that all persons assisting with the research are adequately informed about the protocol, the research procedures, and their duties and functions.

Response: All study personnel undergo CITI, HIPAA, and other HSIRBrequired training. Additionally, study personnel are required to read through the protocol and develop a good understanding of the study procedures. Additionally, study personnel work together in a collaborative environment to maintain awareness of the study procedures and any learning opportunities that may arise. Additionally, members of the research team meet weekly to discuss study progress, and clear roles as well as individual projects are defined in these meetings.

21.0 Prior Approvals

21.1 Describe any approvals that will be obtained prior to commencing the research. (E.g., school, external site. funding agency, laboratory, radiation safety, or biosafety approval.)

Response: Approval from our funding body, Dent Family Foundation, was required.

22.0 Recruitment Methods

22.1 Describe when, where, and how potential subjects will be recruited.

Response: Recruitment strategies include an advertisement in the once monthly issue of an After 50 free newspaper. If needed, the study will also be investing in 32 sixty-second radio advertisements and 50 sixty-second streaming commercials for two weeks. Additionally, the study hopes to recruit from the current patient population at the Dent Dizziness and Balance Center. However, we will avoid infringing on the privacy rights of both former and current patients by only allowing the principal investigator, who is the clinic doctor, and other study staff involved with the Dent Dizziness and Balance Center to reach out to patients. We believe this is ethical because [name] and the clinic staff already have access to any potential participants' medical history and it would prevent other study staff from gaining access to medical information before the start of the study and without the participant's direct consent.

22.2 Describe the source of subjects.

Response: Individuals who read After 50 or are in the WNY area, already within the existing database, or in any way comes into contact with Dent or our advertisements, has Meniere's Disease and is eligible and wants to participate.

22.3 Describe the methods that will be used to identify potential subjects.

Response: Potential subjects will be identified first by [name] if they meet criteria for a Meniere's disease diagnosis and meet basic eligibility criteria. Participants who indicate interest in participating in the study will then review the consent form and additional eligibility criteria with either the study coordinator or another member of the research team. The participant is given the option to take the form home to think about it or sign it at that time if they are certain they want to participate.

22.4 Describe materials that will be used to recruit subjects. (Attach copies of these documents with the application. For advertisements, attach the final copy of printed advertisements. When advertisements are taped for broadcast, attach the final audio/video tape. You may submit the wording of the advertisement prior to taping to preclude re-taping because of inappropriate wording, provided the IRB reviews the final audio/video tape.)

Response: Please see 22.1

22.5 Describe the amount and timing of any payments to subjects.

Response: Participants will be reimbursed \$35 per visit, up to \$315 total (6-8 visits for placebo & Lamotrigine groups, respectively, plus 1 extra visit if needed for a maximum of 9 visits). Payment will be made by check and mailed to the participant's address as written on their signed Declaration of Participation form. Should the participant choose to drop out of the study or the study is terminated, a check will be mailed after

completion of the early termination visit or after completion of the most recent visit prior to dropping out.

23.0 Local Number of Subjects

23.1 Indicate the total number of subjects to be accrued locally.

Response: 12 (all)

23.2 If applicable, distinguish between the number of subjects who are expected to be enrolled and screened, and the number of subjects needed to complete the research procedures (i.e., numbers of subjects excluding screen failures.)

Response: 12 subjects are needed to complete research procedures. Because of the long duration of the study, and based on previous experience with patient follow-up, we anticipate approximately 2-5 dropouts. Additionally, we anticipate approximately 20 people will be consented but not enroll in the study, either due to success with other types of treatment (e.g., water pills) employed by [name] or another provider, changing their minds or seeking treatment elsewhere, or for other unknown reasons.

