Participants who are diagnosed with Ménière's disease, as determined by clinical history, ENT confirmation and an audiogram, will qualify if they also have had two or more Ménière's vertigo attacks in a four-week span for two consecutive four-week periods (the qualification period). Those who meet these criteria will then need two or more Ménière's vertigo attacks during a four-week lead-in period to further establish a baseline and verify randomization eligibility. Participants are allowed from the beginning of the lead-in to take their choice of a symptomatic abortive medication according to its package instructions for Ménière's vertigo attacks that last longer than 30 minutes with nausea and/or vomiting. Symptomatic abortive medications include, but are not limited to, meclizine (Antivert), Valium, diazepam, or Zofran. The abortive medication can be used throughout the study regardless of treatment assignment and its use will be recorded. Twelve eligible participants, with a minimum total of six attacks during the qualification and lead-in periods, will be randomly assigned to either a placebo or lamotrigine treatment group. Randomization will be conducted by UBSoPPS Research Pharmacy. The study drug and matching placebo will be titrated from 25mg twice a day (BID) up to 150mg BID over a six week period. During titration, clinic visits are scheduled every two weeks to assess any adverse events, symptoms, quality of life, and compliance. Those who cannot tolerate the 150mg BID dose may return to a 100mg BID dose during an unplanned visit. However, if a participant is unable to tolerate the 100mg BID dose they will be withdrawn from the study. Participants will maintain the 150mg BID or 100mg BID dose for a 12-week period with clinic visits every four weeks to assess their progress. Between all study visits, participants are asked to complete a daily survey describing their symptoms. This survey is hosted by polleverywhere.com and can be completed through text message, an online website, or with a paper document- whatever method is preferred by the participant. At the conclusion of the 12-week study period, a study staff will be un-blinded

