Response: According to our preliminary data, the mean number of vertigo attacks after 3 months of treatment with Lamotrigine was 4.91 (SD=7.24), and we expect the mean number of vertigo attacks in the placebo group to be approximately 13. We assumed Negative Binomial distribution for the response, two-sided tests, level of significance 0.05 and considered various sample sizes, mean and variance of the number of attacks in the two groups. We calculated the associated power for comparison of the mean response between the two groups by utilizing Monte Carlo simulations and using Negative Binomial regression model with log link. Each simulation consisted of 1000 iterations and was conducted in R (http://www.r-project.org/). This analysis showed that a power above 80% can be obtained with a sample of 12 participants.

Table: Associated Power for Comparison of the Mean Response between Treatment Groups Calculated with Monte Carlo Simulations and Negative Binomial Regression Model with Log Link

Total N	Mean Number	Standard	Mean Number	α	Power
	of Attacks in	Deviation of	of Attacks in	level	
	Lamotrigine	the number of	Placebo group		
	group at the end	attacks	at the end of		
	of the study		the study		
12	5	7.24	13	0.05	57.6
12	5	6	13	0.05	60.6
12	5	4	13	0.05	86.6
12	6	6	13	0.05	58.2
12	6	4	13	0.05	83.5
14	5	7.24	13	0.05	60.7
14	5	6	13	0.05	70.1
14	5	4	13	0.05	92.8
20	5	7.24	13	0.05	67.6
20	5	4	13	0.05	97.6
20	5	7.24	12	0.05	60.4
20	5	4	12	0.05	94.5
20	6	7.24	12	0.05	48.8
20	6	4	12	0.05	91.9
34	5	7.24	13	0.05	82.2
34	5	6	13	0.05	92.5

Update on 6/4/2015:

As of 6/4/2015		
Expected N complete		
Complete		
Currently enrolled		
Potentially eligible, not enrolled		
Screened & eligible but declined participation in study		
Screened and ineligible		
Started study but dropped out		
TOTAL		

We engage in a multi-step process to reduce drop-outs, however, this is a very long study (6 months), and some drop-outs are to be expected. Thus far, we've had 2 participants drop out of the study and 8 have completed. Therefore, our dropout rate is 25%. To compensate for drop-outs, we request to increase our enrollment by 25%, rounded to the nearest whole number attain equal numbers in each group, for a total N of 16.

11.3 Describe the steps that will be taken secure the data (e.g., training, authorization of access, password protection, encryption, physical controls, certificates of confidentiality, and separation of identifiers and data) during storage, use, and transmission.

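### Section 23 accrues 12 but needs 12 completers after 2-5 dropouts, and the 16 requested in Section 11.2 was not carried into the rest of the plan

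*Combined protocol and SAP*

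**What the plan says.** Section 23.1 gives the number to be accrued locally as 12, which is the whole study. Section 23.2 states that "12 subjects are needed to complete research procedures" and, because the study is long, that "we anticipate approximately 2-5 dropouts". It does not say how many will be randomised.

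Section 11.2 rests the design on the statement that "a power above 80% can be obtained with a sample of 12 participants". Its update of 6/4/2015 reports 2 dropouts and 8 completers, calls this a 25% dropout rate, and asks to raise enrolment to compensate, "for a total N of 16", with equal groups.

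The other sections keep the smaller number:
- Section 9.1 randomises "Twelve eligible participants, with a minimum total of six attacks during the qualification and lead-in periods".
- Section 12.7 describes the study as n=12.
- Section 20.2 says "we believe it is reasonable to obtain the 12 participants".
- Sections 9.4 and 30.1 have the pharmacist generate 12 allocations.

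Section 3.2 replaces people who leave before randomisation. No section replaces a randomised participant who leaves. Sections 3.2 and 9.2 count a participant as enrolled from randomisation at Visit 2, so the 16 in Section 11.2 reads as 16 randomised.

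**The concern.** A reader cannot tell from the plan whether 12 or 16 people will be randomised. Section 23 conflicts with itself, and its total conflicts with Section 11.2. The allocation list is the operational document, and it has no entry for a thirteenth participant.

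The stake is the number available for the primary comparison. The power simulation in Section 11.2 describes no dropout, so its 12 is 12 people with an end-of-study count. Section 13.3 collects nothing further after a participant withdraws, and Section 11.1 gives no rule for a missing end-of-study count in the rank-sum test. If enrolment followed the un-updated figure, the comparison would probably have fewer people than the power statement assumes.

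**Working it through.** **Inputs.** Accrual 12 (Section 23.1); completers needed 12 and dropouts 2-5 (Section 23.2); updated total 16, with 2 dropouts and 8 completers to date (Section 11.2); two-sided 0.05; means 5 v 13 with SD 4, the most favourable N=12 row of the power table.

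**1. The plan's own figures.**
- Enrolment: 12 x 1.25 = 15, made even for equal groups = 16. Dividing instead, 12/(1 - 0.25) = 16.
- The 25% is 2/8. Among those with a known outcome the rate is 2/10 = 20%, and 12/0.80 = 15, again 16 when made even. The 16 stands either way.
- Power: the table gives 86.6% for this row. Negative binomial regression with log link, equal SD in both arms and 1000 iterations gave 84.8-86.5% (likelihood ratio) and 89.3-89.9% (Wald). The row is reproduced.

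**2. Section 23 on its own.**
- Completers if accrual stops at 12: 12 - 5 = 7 to 12 - 2 = 10.
- Randomised needed for 12 completers: 12 + 2 = 14 to 12 + 5 = 17.

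**3. With the 16 of Section 11.2.**
- Completers: 16 - 5 = 11 to 16 - 2 = 14.
- At the stated 25% rate: 16 x 0.75 = 12.
- The target of 12 is met with up to four dropouts and missed by one with five.

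**4. Power by number of completers.** Same row, losses split as evenly as possible, leavers without an end count. Ranges cover repeated simulations for the rank-sum test, and likelihood ratio to Wald for the regression.

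| Completers | Split | Exact rank-sum, end counts | Negative binomial regression |
|---|---|---|---|
| 7 | 3 v 4 | 9-10% | 73-78% |
| 10 | 5 v 5 | 72-73% | 80-84% |
| 11 | 5 v 6 | 76-78% | 85-89% |
| 12 | 6 v 6 | 82% | 85-90% |
| 14 | 7 v 7 | 89-91% | 89-91% |

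At 3 v 4 the smallest untied two-sided rank-sum p is 2/C(7,3) = 2/35 = 0.057, so significance there is possible only through ties.

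Two limits apply. Section 11.1 applies the rank-sum test to the reduction from baseline, whereas the simulation uses end counts, because the plan gives no baseline-to-end correlation. The row is also the favourable one: with SD 7.24 the plan's table gives 57.6% at N=12 and 60.7% at N=14.

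**The case against.** The strongest reply is that the plan has already dealt with dropouts. The 6/4/2015 update raises enrolment to 16 for that reason, and 16 is the correct inflation of 12 at 25%. This stands, and it rules out a stronger reading that Section 23 invites: that the trial will end with 7-10 completers. That follows only if accrual stops at the un-updated figure. The update is worded as a request, however, and the documents do not show its approval, so the two figures still have to be reconciled.

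A reader might also infer that the primary test has almost no chance of success. The documents do not support this. It needs accrual stopped at 12, all five dropouts, a 3 v 4 split and no usable end count from any leaver. Part of the fall also comes from replacing the regression used for the power table with an exact rank-sum test.

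Completers are not exactly the analysed number. Section 11.1 includes everyone randomised who took a dose and adds a longitudinal mixed model that can use diary data from leavers. Sections 9.2 and 13.2 provide early termination visits for several kinds of withdrawal. That softens the loss but supplies no end-of-study count for the rank-sum comparison.

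The form's prompt in Section 23.2 glosses the number needed as the number excluding screen failures, so the 12 could be read as the number randomised. That would reconcile Sections 23.1 and 23.2. It would not reconcile either with Section 11.2, which inflates 12 for dropouts and so treats it as the number to finish.

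The pilot cannot settle the dropout rate. Section 2.2 reports ten lost and four stopped, 14/48 = 29%, without saying when, and 35 completed the initial follow-up. It does not show a 29% loss by that visit.

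**Conclusion.** The sample size is wrong as written and should be corrected. Section 23.1 falls 2-5 short of what Section 23.2 needs, and it is 4 below the total requested in Section 11.2. The smaller figure also remains in Sections 9.1, 12.7 and 20.2 and in the allocation list in Sections 9.4 and 30.1. This is an update not carried through, rather than a trial set to miss its target.

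With 16 randomised, the plan's own dropout range leaves 11-14 completers, and 12 is missed only at the upper end, by one. The corresponding power is roughly 77-90% on the favourable row. That range assumes leavers contribute no end-of-study count, the groups are equal, losses are nearly balanced, and end counts stand in for the reduction from baseline. The figure of 7-10 completers applies only if the increase was not approved.

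**What to change.** If the increase to 16 was approved:
- Replace 12 with 16 randomised in Sections 23.1, 9.1, 12.7 and 20.2.
- In Sections 9.4 and 30.1, have the pharmacy generate 16 allocations in equal groups.
- In Section 23.2, state 16 randomised and 11-14 expected completers.
- In Section 11.2, quote power for 11-14 completers rather than for a fixed 12, and name the test and the table row used.

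If it was not approved, keep 12, restate the expected completers as 7-10, and give the power at those numbers.

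The cost is text edits and four more allocation entries (16 - 12 = 4). Nobody is enrolled beyond the 16 already requested. The stated power becomes a range with a less favourable lower end.
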